- Questionnaire: age, educational level, previous breast cancer, perceived risk of breast cancer, breast cancer worry, breast cancer among family/friends, previous mammogram, intended participation (and stage of decision making for one of three groups), reading health information in general, having read the leaflet about breast cancer screening (link in the invitation letter to this study), being more positive/negative about screening after having read breast cancer screening information, being more/less willing to participate after having read breast cancer screening information, indicating that screening participation is their very own decision vs. indicating that you should follow recommendations from health authorities about screening participation (two questions), indicating that they prefer to make their own decision about screening participation based on own attitudes and values and the information available vs. indicating that they prefer that health authorities recommend whether they should participate or not (two questions), and preferences for future screening invitation.

Hypothesis and aims

Main hypothesis: The majority of Danish women have made the decision about breast cancer screening participation prior to invitation and presentation of screening information. More specifically, the main hypothesis for this study is that 80% of Danish women have already made their decision when presented to the opportunity framing and 70% when presented to the choice framing.

To investigate the main hypothesis above, the following analyses will be performed, where subheadings indicate the theme addressed by the analyses:

Screening decision made prior to reading information

- Estimate prevalence of women who have made the decision to participate in breast cancer screening across randomization groups and for each of the two framings. Intended participation is answered on 5-point Likert scale and will be dichotomized as participation (two categories) and non-participation/unsure (three categories).
- Compare prevalence of women who have made the decision depending on opportunity vs. choice framing with chi-squared test.

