- Crude and adjusted* logistic regression with intended participation as outcome and framing as independent categorical variable. The group receiving “Stage of decision making” is included in this analysis for comparison. Intended participation is answered on 5-point Likert scale and will be dichotomized as participation (two categories) and non-participation/unsure (three categories).
- Sensitivity analyses restricting intended participation to only one category for all analyses (only “Yes, I want to participate” and not “I think I want to participate”).

Stage of decision making

- Estimate prevalence of women in each decision stage based on “Stage of decision making”.
- Crude and adjusted* logistic regression with intended participation as outcome and “Stage of decision making” as independent continuous variable.

Aim 1: Women do not take the presented screening information into account when making their decision about participation.

To investigate aim 1, the following analyses will be performed, where subheadings indicate the theme addressed by the analyses:

Different framing

- Same analyses as for main hypothesis – does framing make a difference (and is information taken into account)?

Do women read health information

- Estimate prevalence of women who read health information in general and who have read the breast cancer screening information specifically.
- Crude and adjusted* logistic regression with participation as outcome and reading information (in general + screening related) as independent variables.

More or less positive/negative after reading information

- Estimate prevalence of women who are more or less positive/negative depending on previously intended participation and framing, respectively.

- Crude and adjusted* logistic regression with more or less positive/negative as outcome and intended participation and framing as categorical independent variables.

Dichotomization of outcome depends on results**

More or less willing to participate after reading information

- Estimate prevalence of women who are more or less willing to participate depending on previously intended participation and framing, respectively.
- Crude and adjusted* logistic regression with more/less willing as outcome and intended participation and framing as categorical independent variables.

Dichotomization of outcome depends on results**

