Aim 2: Women think of the screening participation as less of an actual (individual) choice and more of something to comply with when invited.

To investigate aim 2, the following analyses will be performed:

- Estimate prevalence for each of the two statements (indicating that screening participation is their very own decision vs. indicating that you should follow recommendations from health authorities about screening participation) for all five categories (5-point Likert scale, "strongly agree" – "strongly disagree").
- 2x2 table of seeing it as individual choice vs. recommendation to comply with ("strongly agree" and "agree" for both statements).
- Crude and adjusted* logistic regression with thoughts on screening participation as outcome and intended participation and framing as categorical independent variables.

Thoughts on screening participation is a dichotomized variable based on the two statements mentioned above. Women are categorized as "individual choice" when they answer "agree" or "strongly agree" to the first statement and answer "neutral", "disagree", or "strongly disagree" to the other statement (coded 0). In contrast, women are categorized as "recommendation to comply with" when they answer "agree" or "strongly agree" to the second statement and answer "neutral", "disagree", or "strongly disagree" to the other statement (coded 1). Inconsistent responses to the two statements and disagreement towards both statements are coded as missing and their frequency reported.

Aim 3: Women do not want to make an informed decision about their own health (and be responsible for their own health).

To investigate aim 3, the following analyses will be performed:

- Estimate prevalence for each of the two statements (indicating that they prefer to make their own decision about screening participation based on own attitudes and values and the information available vs. indicating that they prefer that health authorities recommend whether they should participate or not) for all five categories (5-point Likert scale, "strongly agree" – "strongly disagree").
- 2x2 table of wanting informed decision making vs. health authorities make recommendation ("strongly agree" and "agree" for both statements).

- Crude and adjusted* logistic regression with preference for decision making as outcome and intended participation and framing as categorical independent variables.

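### The Aim 2 and Aim 3 regressions keep only women who agree with exactly one of two separately asked statements, so the only stated framing comparison is made in subsets selected on the outcome

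*SAP*

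**What the plan says.** The list of available variables in the SAP Introduction shows that the Aim 2 statements are separate items: "indicating that you should follow recommendations from health authorities about screening participation (two questions"). The Aim 3 pair is described in the same way.

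Under Aim 2 and Aim 3 the regression outcome is 0 if a woman agrees (or strongly agrees) with the first statement and is neutral or disagrees on the second. It is 1 in the mirror-image case. For the rest, both sections say: "Inconsistent responses to the two statements and disagreement towards both statements are coded as missing and their frequency reported".

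Randomised framing is a predictor in both models: "Crude and adjusted* logistic regression with thoughts on screening participation as outcome and intended participation and framing as categorical independent variables" for Aim 2, and "Crude and adjusted* logistic regression with preference for decision making as outcome and intended participation and framing as categorical independent variables" for Aim 3.

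Each aim also has five-category prevalences for each statement and a cross-tabulation, for Aim 2 a "2x2 table of seeing it as individual choice vs. recommendation to comply with". Neither is stated to be split by framing. Under Aim 1 the SAP does state such a split: "Estimate prevalence of women who are more or less willing to participate depending on previously intended participation and framing, respectively".

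**The concern.** With two separate questions, agreeing with both or with neither is a valid answer. A woman may hold that screening is her own decision and also that official advice should be followed. She may want to decide for herself and still welcome a recommendation. The 2x2 table treats agreement with both as something to report; the regression treats it as missing data.

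The exclusion is decided by the outcome items, which are answered after randomisation. If framing shifts women into or out of the both and neither groups, the arms contribute differently selected women, and the odds ratio compares those subsets rather than the arms as randomised. It could then be read as a move from own choice towards compliance that neither statement shows. It could equally hide a change in both statements. A single overall frequency of excluded answers would not show whether exclusion differs by arm.

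There is also a gap in the coding. Pairs that are neutral on both statements, or neutral on one and disagreeing on the other, fit neither code and are not named in the missing rule. It is unclear whether they count in the reported frequency.

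**Working it through.** **Inputs.** From the SAP: the coding rule and the five-point scales (Aims 2 and 3). The SAP gives no agreement rates, sample size or expected excluded share, so there is no figure of its own to reproduce. All percentages below are assumptions chosen to show the mechanism. The odds ratios are unadjusted and compare two arms.

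**Step 1: the answer grid.** The 5 × 5 = 25 answer pairs divide as follows (cells, not women):

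| Answer pair | Cells | Regression outcome |
|---|---|---|
| Agrees with first only | 2 × 3 = 6 | 0 |
| Agrees with second only | 3 × 2 = 6 | 1 |
| Agrees with both | 2 × 2 = 4 | missing |
| Disagrees with both | 2 × 2 = 4 | missing |
| One neutral, one disagree | 4 | fits no code, not named |
| Neutral on both | 1 | fits no code, not named |

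So 12 pairs enter the model and 13 do not.

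**Step 2: formulas.** Let pA and pB be the shares agreeing with the first and second statement, and t the share agreeing with both. Then:
- first only = pA − t; second only = pB − t; neither = 1 − pA − pB + t
- odds modelled by the SAP = (pB − t)/(pA − t)
- share excluded = 2t + 1 − pA − pB, which lies between |1 − pA − pB| and 1 − |pA − pB|

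**Step 3: same agreement in both arms, different overlap.** Take pA = 0.70 and pB = 0.60 throughout, so a model of either statement gives an odds ratio of 1.

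| t | First only / second only / both / neither (%) | Odds | OR v t = 0.40 | Analysed |
|---|---|---|---|---|
| 0.40 | 30 / 20 / 40 / 10 | 20/30 = 0.667 | 1.00 | 50% |
| 0.45 | 25 / 15 / 45 / 15 | 15/25 = 0.600 | 0.90 | 40% |
| 0.50 | 20 / 10 / 50 / 20 | 10/20 = 0.500 | 0.75 | 30% |

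If the arms are identical the odds ratio is 1. If pA = pB in both arms the odds are 1 at any t, so the odds ratio again stays at 1.

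**Step 4: the reverse problem.** Take 30/20/30/20 in one arm and 24/16/45/15 in the other. Agreement with the first statement rises from 60% to 69%, and with the second from 50% to 61% (odds ratio (0.61/0.39)/(0.50/0.50) = 1.56). The SAP's odds ratio is (16/24)/(20/30) = 1.00. A real change in both statements would not be seen.

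**Step 5: how much could be excluded.**
- 70%/30% agreement: 0% to 60%
- 70%/50% agreement: 20% to 80%
- 80%/60% agreement: 40% to 80%

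**Step 6: would it be noticed?** For 30/20/40/10 v 20/10/50/20, the standard error of the log odds ratio with 100 respondents per arm is √(1/30 + 1/20 + 1/20 + 1/10) = 0.483. With ln 0.75 = −0.288, the expected |z| reaches 1.96 at 100 × (1.96 × 0.483/0.288)² ≈ 1,083 respondents per arm (unrounded inputs). For the smaller shift the standard error is √(1/30 + 1/20 + 1/25 + 1/15) = 0.436, and with ln 0.90 = −0.105 the number is about 6,600 per arm.

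**The case against.** The strongest reply is that Aims 2 and 3 are descriptive statements about women in general. The five-category prevalences and the 2x2 table answer them in all respondents, and framing is only one of two named predictors in a secondary regression. The rule is fixed in advance and the number excluded is reported. A test of no framing effect on these answers remains valid. The illustrations are constructed, and even the larger shift needs about 1,083 respondents per arm to have roughly an even chance of significance. Finally, the second-only v first-only contrast from a four-level multinomial model is the same crude odds ratio, (10/20)/(20/30) = 0.75, so the remedy partly reproduces what is criticised.

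Much of this stands. The descriptive aims are covered, the null is preserved, and the size is unknown. In the example framing does change the joint answers, so 0.75 is a true ratio of categories; the problem is how it would be read. Reporting agreement with both in a table while leaving it out of a model is not in itself a contradiction.

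It does not remove the point. Fixing a selection rule in advance does not make the selected subsets comparable once framing has an effect. The all-respondent summaries are not stated by framing, so they do not supply the missing comparison. The multinomial model adds what the present one cannot show: in the same example, both v first only gives (50/20)/(40/30) = 1.88 and neither v first only gives (20/20)/(10/30) = 3.00.

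**Conclusion.** The concern holds. The regressions for Aims 2 and 3 analyse exactly the women who agree with one statement only, and no framing comparison over all respondents is stated for either aim. The resulting odds ratio is valid as a conditional contrast and has expected value 1 if framing changes no answers. It is not a reliable measure of a shift from own choice to compliance if framing alters how many women agree with both or neither.

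The size cannot be derived from the SAP. Under the assumed 70%/60% agreement, overlap shifts of 5 and 10 percentage points give odds ratios of 0.90 and 0.75 where each statement's own odds ratio is 1. The excluded share could be anywhere from 0% to 80% across the agreement rates tried. The point should be corrected, but it concerns secondary analyses and leaves the main hypothesis untouched.

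**What to change.** For each of Aims 2 and 3:

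- Add one regression in all respondents to the two statements. This can be a four-level multinomial model (first only, second only, both, neither including neutral pairs) or a logistic model for each statement (agree or strongly agree v the rest). The multinomial model also detects a change in overlap when agreement with each statement is unchanged; the separate logistic models do not.
- Report the 2x2 table and the excluded share by framing arm.
- State where neutral-neutral and neutral-disagree pairs are counted.
- Keep the present 0/1 contrast, labelled as conditional on agreeing with exactly one statement.

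The cost is SAP wording and one extra model per aim (two if each statement is modelled separately), using answers the questionnaire already collects. The downside is a longer result to report than a single odds ratio.

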Investigating Barriers for Decision Making in a Danish Breast Cancer Screening Context

Statistical Analysis Plan

NCT05444725

Unique Protocol ID: 2016-051-000001, 2563

Date: August 23, 2022

Statistical analysis plan

Introduction

Informed decision making and the use of decision aids are often recommended in breast cancer screening. However, informed decision making might be challenged by *ex ante* positive attitudes towards screening. Several studies have found high levels of enthusiasm towards screening including one of our own studies in a Danish breast cancer screening context (unpublished). Therefore, we will investigate preferences and attitudes towards breast cancer screening, invitation, and decision making among Danish women in this study. The study will be conducted by sending out an online questionnaire to women aged 44-49 in Denmark. Women will be randomized to one of three versions of the questionnaires: 1) Questionnaire with "Stage of Decision Making"-question to investigate women's decision making process regarding participation in screening (by asking whether women have made their decision about participation or not based on six different options of decision stages), 2) Questionnaire with choice framing (presentation of a choice between participation in breast cancer screening or no screening), or 3) Questionnaire with opportunity framing (only presentation of screening, no alternative) to investigate the decision making process and the impact of different framing. Next, women are asked to state their intended participation in screening on a 5-point Likert scale.

Subsequently, questionnaire data will be linked to register data on sociodemographic factors from Statistics Denmark.

The following variables are available:

- Register data: educational level, socioeconomic status (based on employment), civil status, municipality, and whether the person was immigrant, descendant (born in Denmark by foreign parents) or of Danish origin.

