Preference for decision making is a dichotomized variable based on the two statements mentioned above. Women are categorized as “wanting informed decision making” when they answer “agree” or “strongly agree” to the first statement and answer “neutral”, “disagree”, or “strongly disagree” to the other statement (coded 0). In contrast, women are categorized as “health authorities make recommendation” when they answer “agree” or “strongly agree” to the second statement and answer “neutral”, “disagree”, or “strongly disagree” to the other statement (coded 1). Inconsistent responses to the two statements and disagreement towards both statements are coded as missing and their frequency reported.

At the very end of the questionnaire, women are asked about their preferences for future screening invitation (how and what material is sent at invitation regarding invitation letter, information leaflet and pre-scheduled time for screening). For this question, four pre-defined options are suggested based on the current Danish invitation strategy and, lastly, a text field is provided for other suggestions and thoughts. Based on these responses, prevalences can be estimated for the four pre-defined invitation strategies. Next, responses provided in the text field can be investigated and possible themes and other strategies can be identified. This can be important knowledge for future research and administration of the Danish breast cancer screening program.

* The following variables are used as independent variables in adjusted analyses: educational level, socioeconomic status (based on employment), civil status, whether the person was immigrant, descendant (born in Denmark by foreign parents) or of Danish origin, perceived risk of breast cancer, breast cancer worry, and previous mammogram.

** Because women are generally very positive about screening and want to participate in screening, we hypothesize that it is more likely that women will be more negative and less willing to participate after reading screening information than becoming even more positive and more willing. This is because we assume that it is difficult to be much more positive and more willing to participate than is already the case.

If this hypothesis is true, the responses will be dichotomized as follows:

Positive/negative: Focus is on women being more negative, therefore, the two “negative” responses will be coded as 1 and the two “positive” responses and “unchanged” will be coded as 0.

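### Age is collected but left out, without a reason, of the one covariate list behind every adjusted model, so the models with non-randomised exposures can carry avoidable age confounding

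*SAP*

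**What the plan says.** The SAP Introduction describes the sample: "The study will be conducted by sending out an online questionnaire to women aged 44-49 in Denmark". Its list of available variables puts age first among the questionnaire items: "Questionnaire: age, educational level, previous breast cancer, perceived risk of breast cancer".

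Each adjusted regression is marked with an asterisk that leads to a single footnote. The footnote opens "The following variables are used as independent variables in adjusted analyses: educational level, socioeconomic status (based on employment), civil status" and ends "or of Danish origin, perceived risk of breast cancer, breast cancer worry, and previous mammogram". That makes seven variables: education, socioeconomic status, civil status, origin, perceived risk, worry and previous mammogram. Age is not one of them, and the SAP does not say why.

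The prevalence analyses do not use age either. Under the main hypothesis the plan is to "Estimate prevalence of women who have made the decision to participate in breast cancer screening across randomization groups and for each of the two framings". For the arm asked about decision stage it is to "Estimate prevalence of women in each decision stage based on “Stage of decision making". No prevalence in the later aims is broken down by age.

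**The concern.** Most of the adjusted regressions do not rest on randomisation. Their exposures are things women report about themselves: how far they have got in deciding, whether they read information, and whether they intend to take part. In these models adjustment is the only protection against confounding.

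Age is a natural candidate. It is fixed before any answer is given, and the questionnaire version cannot change it. It could be related to reading, decidedness, intention and attitude together. The plan adjusts for civil status and employment but not for age, although age is already in the data. At stake is whether an adjusted odds ratio, for example of participation on reading, reflects reading or partly the fact that readers and non-readers differ in age.

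A lesser matter is description. If decidedness varies across the six years, the pooled percentage depends on the age mix of those who respond, and no planned table would show it.

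**Working it through.** **1. Text check.** The SAP states no sample size, power or age effect, so there is no figure to reproduce. The models marked as adjusted divide as follows.

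- Randomised exposure only: intended participation on framing (main hypothesis).
- Non-randomised exposure: intended participation on decision stage; participation on reading information (Aim 1); change towards positive or negative on intended participation (Aim 1); change in willingness on intended participation (Aim 1); thoughts on participation on intended participation (Aim 2); decision preference on intended participation (Aim 3). The last four also include framing.

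All seven use the same footnote, and age is absent from it.

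**2. Possible size of the confounding (assumed gradients).** Take equal numbers at ages 44, 45, 46, 47, 48 and 49 (mean 46.5). The variance of age is (2.5² + 1.5² + 0.5² + 0.5² + 1.5² + 2.5²)/6 = 17.5/6 = 2.917. Suppose that exposure and outcome are unrelated within each year of age, and that the odds of each change by a factor g per year. The spurious odds ratio is then approximately exp[(ln g)² × 2.917].

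- g = 1.0: exp(0) = 1.00
- g = 1.1: exp(0.00908 × 2.917) = exp(0.0265) = 1.03
- g = 1.2: exp(0.0332 × 2.917) = exp(0.0970) = 1.10
- g = 1.3: exp(0.0688 × 2.917) = exp(0.2008) = 1.22

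An exact calculation, averaging the two-by-two cell probabilities over the six ages, gives 1.03, about 1.10 and about 1.21 for the last three. It hardly depends on how common exposure and outcome are (tried at 30% to 80% and 70% to 80%). Opposite gradients would give the reciprocals. Covariates already in the footnote that vary with age would absorb part of this.

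**3. The randomised framing contrast.** The SAP hypothesises "80% of Danish women have already made their decision when presented to the opportunity framing and 70% when presented to the choice framing". The marginal odds ratio is (0.80/0.20)/(0.70/0.30) = 1.714. With the same assumed gradients, the age-conditional odds ratio is 1.719 (g = 1.1), 1.731 (1.2) or 1.748 (1.3). The risk difference stays at 10 points. The small shift arises because the odds ratio is not collapsible; it is not bias.

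**4. What the pooled prevalence would average over.** Under a logistic gradient with equal ages, the values at age 44 and age 49 are as follows.

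| OR per year | Pooled 80% | Pooled 70% |
|---|---|---|
| 1.0 | 80% and 80% | 70% and 70% |
| 1.1 | 76.1% and 83.7% | 64.9% and 74.9% |
| 1.2 | 72.3% and 86.7% | 60.1% and 79.0% |
| 1.3 | 68.8% and 89.1% | 55.8% and 82.4% |

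Every value exceeds 50%, so a majority would hold at each age in these scenarios. If respondents were skewed to older ages (weights 1, 1, 1, 1, 2, 3 from 44 to 49), the pooled 80% would become 81.1%, 82.0% or 82.7% at odds ratios of 1.1, 1.2 and 1.3.

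**The case against.** The strongest reply is that this is a preference about covariates. The list is clear and prespecified, the sample already spans only six years, and perceived risk, worry and previous mammogram may carry part of any age effect. Nothing in the SAP shows that age confounding remains after those adjustments. This stands as a limit on severity: the calculation above gives a negligible effect for weak gradients and none if age is unrelated to either side. It does not explain why a collected variable that precedes every answer is left out.

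A reader might also infer something larger: that age fixes how close each woman is to her invitation, so a hypothesis about deciding before invitation cannot be answered by an average over ages 44-49. The wording "The majority of Danish women have made the decision about breast cancer screening participation prior to invitation and presentation of screening information" makes this tempting, but the SAP does not support it. It never states the age at invitation and never links age to time until invitation. It then specifies the hypothesis as a proportion decided when each framing is presented, without an age qualifier, and the pooled proportion answers that. The item on future invitations asks how they should be designed, not when a woman will receive one.

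Nor is the hypothesised 80% v 70% difference threatened by an age spread of similar size. Framing is randomised, so age is balanced across versions in expectation, and neither the chi-squared comparison nor the framing coefficient is biased by leaving it out.

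**Conclusion.** The point holds for the observational models. Age is available and is missing, without a reason, from the only list that governs adjustment; six regressions have non-randomised exposures that age could confound. Under the assumed gradients of 1.0 to 1.3 per year on both sides, a true null would be shifted to an odds ratio between 1.00 and about 1.2. The true gradient is unknown and may be zero, and part of it may be removed by the existing covariates.

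The randomised framing comparison and the pooled 44-49 prevalence stand as planned. An age breakdown would help interpretation but would not correct an error. Any reading of age as nearness to invitation is an assumption that the document does not supply. Severity is minor to moderate, and the improvement is almost free.

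**What to change.** Add age in single years to footnote * for all adjusted models. Add one descriptive table giving the decided/intended prevalence and the distribution of decision stages by year of age, with confidence intervals, beside the pooled 44-49 figure. The pooled figure stays the main estimate.

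The main hypothesis should not be moved to women aged 49. That would change the quantity estimated and, with equal ages, rest it on one sixth of the sample, with standard errors about √6 ≈ 2.4 times larger.

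The cost is one phrase and one table. No new data are needed. The single-year prevalences will have wide intervals and should be labelled descriptive.

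### The Aim 1 regression of intended participation on reading pools the randomised questionnaire versions without a version term; the leaflet odds ratio carries a small framing effect if version changed leaflet reading or its reporting

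*SAP*

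**What the plan says.** The Introduction describes the design: "Women will be randomized to one of three versions of the questionnaires". One version carries the Stage of Decision Making question, one a choice framing and one an opportunity framing. The intention item follows directly.

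The main hypothesis is that "80% of Danish women have already made their decision when presented to the opportunity framing and 70% when presented to the choice framing". The SAP measures this by intended participation, dichotomised as the upper two of five categories against the other three. It gives no expected percentage for the Stage of Decision Making version.

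Under Aim 1, *Do women read health information*, the plan is: "Crude and adjusted* logistic regression with participation as outcome and reading information (in general + screening related) as independent variables". I take participation here to mean intended participation, because no attendance data are listed among the available variables. No restriction to one version is stated.

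The footnote on adjusted analyses reads "The following variables are used as independent variables in adjusted analyses: educational level, socioeconomic status (based on employment), civil status" and continues with origin, perceived risk, worry and previous mammogram. Questionnaire version is not listed.

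The next model under Aim 1 does include it: "logistic regression with more or less positive/negative as outcome and intended participation and framing as categorical independent variables". So do the model for willingness, the models for Aims 2 and 3, and the main intention model.

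On timing, the variable list says that the leaflet link was in the letter inviting women to the study. The SAP does not say when the leaflet was to be read. Its Aim 1 wording on the change items treats intention as stated before reading.

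**The concern.** The reading model is the only regression spanning several randomised versions that has no version term. The Stage of Decision Making model also lacks one, but that item exists in one version only. The outcome of the reading model is the one the SAP expects the version to move.

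A factor that moves the outcome distorts an exposure odds ratio only if it is also related to the exposure. Leaflet reading is self-reported in the questionnaire, and the link remains available in the letter. A woman shown a choice could open the leaflet before reporting that she had read it, or the framing could colour her report. Version would then lie behind both reading and intention, and part of the pooled leaflet odds ratio would reflect framing.

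What is at stake is one secondary association under Aim 1. In addition, leaflet reading is a direct measure of whether information was used, and the SAP plans no comparison of it across the randomised versions.

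**Working it through.** The SAP gives no sample size, power or expected reading share, so there is no design figure to reproduce. The check asks how far the pooled odds ratio moves when version is left out.

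**Inputs from the SAP.** Intention is 0.80 under opportunity and 0.70 under choice. The difference is 10 points and the odds ratio is (0.80/0.20)/(0.70/0.30) = 1.71.

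**Assumptions.** The two framing groups are equal in size, reading has no effect on intention within either version, and the reading shares are r_o (opportunity) and r_c (choice). The SAP gives no reading shares, so a range is shown.

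**Formula.** Collapse the two tables over version:

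- readers who intend: a = 0.8 r_o + 0.7 r_c
- readers who do not: b = 0.2 r_o + 0.3 r_c
- non-readers who intend: c = 0.8(1 − r_o) + 0.7(1 − r_c)
- non-readers who do not: d = 0.2(1 − r_o) + 0.3(1 − r_c)
- pooled odds ratio = (a/b)/(c/d)

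**Example, 30% v 40%.** a = 0.24 + 0.28 = 0.52; b = 0.06 + 0.12 = 0.18; c = 0.56 + 0.42 = 0.98; d = 0.14 + 0.18 = 0.32. The pooled odds ratio is (0.52/0.18)/(0.98/0.32) = 2.889/3.063 = 0.943.

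**Range, true odds ratio 1.00 within each version:**

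| Reading, opportunity v choice | Pooled odds ratio |
|---|---|
| equal (40% v 40%) | 1.00 |
| 40% v 45% | 0.97 |
| 40% v 50% | 0.95 |
| 30% v 40% | 0.94 |
| 30% v 50% | 0.90 |
| 20% v 40% | 0.88 |
| 40% v 30% | 1.06 |
| 50% v 30% | 1.12 |

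With version in the model, each row returns to 1.00.

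**Third version.** Its intention and reading shares both have to be assumed. With intention between 60% and 90% and three equal groups, the 40% v 50% case gives 0.92 to 0.97. The widest 20-point results come from setting its intention at 90% and its reading equal to the opportunity group's: 0.84 for 30% v 50% and 1.19 for 50% v 30%.

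**A true effect of reading.** With a within-version odds ratio of 2.00 and 40% reading in both framings, the pooled value is 1.98, which is non-collapsibility alone. With 40% v 50% it is 1.86.

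**The case against.** The strongest reply is that version is randomised and so is independent of any reading done before it was shown. The only place given for the leaflet link is the invitation letter, which reaches the woman before the questionnaire. For version to drive reading, she must see the framing, return to the letter, open the leaflet and come back to report it; otherwise the framing must change her report. The SAP describes no such sequence. This stands, and it makes the bias conditional.

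The scope is also narrow. General reading of health information is a habit that one framing is unlikely to move, so the concern applies to the leaflet item. The 10-point expectation covers two of the three versions. Both limits stand.

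If reading did follow the version, it may also have followed the intention item. The exposure would then come after the outcome, and intention could drive reading. That would be the larger problem, and a version term does not cure it. This stands too.

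Finally, framing is an exposure of interest in the neighbouring models, while the footnote lists background characteristics. Leaving a randomised factor out of a model built for another exposure is therefore not a contradiction. That is fair, and it is why the point is minor. It does not remove the benefit of a term that costs almost nothing and guards against the case the SAP leaves open.

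A reader might infer that the reading odds ratio is confounded by framing as planned. The documents do not support that: they neither state nor imply that reading differs by version.

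**Conclusion.** The omission is real and its consequence is conditional and small. If leaflet reading does not differ by version, a null odds ratio stays at 1.00 and a version term brings at most a very small gain in precision. If version changed leaflet reading or its reporting by 10 to 20 points, a null leaflet odds ratio becomes about 0.88 to 1.12. This rests on the SAP's 80% and 70%, on equal groups and on assumed reading shares, with the third version left out. Extreme assumptions for the third version widen the range to about 0.84 to 1.19.

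A reader might also infer that comparing reading across versions would settle when the leaflet was read. It would not. Equal shares are compatible with reading after the questionnaire began, for instance reading prompted by the questionnaire itself or by the woman's own intention. A clear difference would show that version affected reading or its reporting; no difference leaves the timing open.

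This is an optional improvement, not an error that threatens the main hypothesis.

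**What to change.** Make three small changes under Aim 1, *Do women read health information*:

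1. Add questionnaire version, as a three-level categorical variable, to the adjusted reading regression. The crude model can stay as planned.
2. Beside the planned reading prevalences, report leaflet reading by version with a chi-squared test, and present it as a randomised comparison bearing on Aim 1.
3. State two limits: the version term does not remove reverse causation if the leaflet was read after the intention item, and similar reading across versions does not show that reading preceded the questionnaire.

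The cost is two model terms, one small table and two sentences, all on data already to be collected. There is no material downside.
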